For the last year, my research group has been enrolling families in a clinical trial evaluating the impact of providing them with daily written summaries of ICU rounds on their experience (NCT03969810). Using validated instruments, we have measured symptoms of anxiety, depression, and acute stress among family members at multiple time points during the ICU stay. During the hospitalization, families also participated in interviews dealing with their experiences. Compared to the 96 family members who were enrolled prior to the COVID-19 pandemic, the 88 family members who have been enrolled during the COVID-19 pandemic were more likely to develop clinically significant depressive symptoms (27% vs. 13%, p=0.03 for difference) and tended to develop clinically significant acute stress symptoms (61% vs 48%, p=0.11 for difference). There were similar levels of clinically significant symptoms of anxiety before and during the COVID-19 pandemic (42% vs. 35%, p=0.43 for difference) (manuscript in preparation). It is likely that restrictions on family visitation and challenges with communication during the COVID-19 pandemic contributed to the high psychological symptom burden among family members during this time period.

The best practices for clinicians to engage with family members in times when they cannot visit their loved ones in the ICU are poorly understood. It is unclear the degree to which families of

COVID-19 patients continue to have psychological symptoms after the patient is discharged and how these symptoms may be impacting quality of life and the patient's recovery. For family members who develop mental health disorders, it is likely that many do not seek out professional help. To address these gaps in knowledge, we propose the following three specific aims.

- 1. To determine the extent to which families of COVID-19 patients have psychological symptoms 3-6 months after the patient was discharged from the hospital.** We will reconsent family members who participated in our initial study during the COVID-19 pandemic. We will conduct one phone interview and use validated instruments to determine the prevalence of anxiety, depression, and post-traumatic stress disorder.
- 2. To determine the characteristics of ICU care delivery during the COVID-19 pandemic that were associated with the development of psychological symptoms among families.** To achieve this goal, we analyze phone interviews conducted during and after the hospitalization. We compare themes among families who developed psychological symptoms to those who did not.
- 3. To determine whether a trauma-focused cognitive behavioral therapy intervention helps reduce the burden of symptoms among family members with psychological symptoms.** We will pilot a program in which family members with clinically significant psychological symptoms will be offered up to six phone/video counseling sessions with mental health professionals. To determine the effect of this therapy, we will conduct phone interviews and use validated instruments to determine the prevalence of anxiety, depression, and post-traumatic stress disorder after the intervention.

Methods

Enrollment

Surrogates of ICU patients with COVID-19 who were enrolled in the study "ICU Rounding Summaries for Families of Critically Ill Patients" (19042604-IRB01) will be approached to participate in a follow-up study dealing with their mental health after patient discharge. We will email and call surrogates to describe the project and provide an informed consent form for them to review.

Inclusion criteria

- The patient's surrogate was enrolled in "ICU Rounding Summaries for Families of Critically Ill Patients" (19042604-IRB01) and the patient had COVID-19
- The patient has been discharged from the hospital

Exclusion criteria

- None

Intervention

Part 1- Post-ICU discharge survey and Interview

Upon enrollment in this post-ICU discharge follow-up study, the subject (surrogate of the ICU patient) will complete a survey dealing with the patient's course since Rush discharge

1. Is the patient still alive?

- a. If deceased, did the patient pass away at Rush or after discharge from Rush?
- b. If alive, is the patient at home?
 - i. If at home, for how long? Is he/she receiving home health services?
- 2. If the patient did not pass away at Rush, did the patient spend time in a rehabilitation hospital, nursing home, or long-term acute care hospital after discharge from Rush?
- 3. Is the patient currently having any of the following symptoms (check all that apply).
 - a. Fatigue
 - b. Trouble Breathing
 - c. Difficulty speaking
 - d. Difficulty eating
 - e. Difficulty thinking or paying attention
 - f. Pain or discomfort
 - g. Anxiety
 - h. Depressed mood
 - i. Difficulty moving or walking
 - j. Difficulty performing activities of daily living such as dressing or bathing
- 4. Have you used mental health services since the time the patient was admitted?
- 5. What is your overall impression of mental health services (choices ranging from very unhelpful to very helpful)

Subjects will be asked to complete the 1) Critical Care Family Needs Inventory (CCFNI) questionnaire, 2) Hospital Anxiety and Depression Scale (HADS), and 3) Impact of Events Scale Revised (IES-R) questionnaire. (**Appendix**)

Subjects will participate in a 30-minute phone interview with a psychologist. The psychologist will review the subject's responses to the above surveys and ask follow-up questions (**Appendix**). The psychologist will ask how the subject has been coping with any psychological symptoms (i.e. anxiety, depression, post-traumatic stress)

The psychologist will describe different types of interventions for people coping psychological symptoms and assess the subject's interest in pursuing any of them.

We will not begin Part 2 until 10 subjects have completed "Part 1- Post-ICU discharge survey and Interview." We will review survey responses and interview transcripts for the first 10 subjects. Based on responses will determine the type(s) of support interventions that will be offered for subjects in this study. An amendment to the study protocol will be made at this time.

Part 2 - Post-ICU psychological intervention

Subjects with clinically significant psychologist symptoms based on either their survey or interview responses will be invited to participate in 6-week trauma-focused intervention with a psychologist.

The program will be brief and delivered online to test the acceptability and feasible of the program, and to gather a preliminary estimate of effect size. We will pilot a group-based intervention (n =3-5) online over Zoom and deliver the intervention across six sessions outlined below. Sessions will last 60-75 minutes depending on participant questions and discussion.

Experiential exercises will be drawn from Acceptance and Commitment Therapy, a related contemporary cognitive behavioral treatment (Hayes, Strosahl, & Wilson, 2012). Some commentary of Viktor Frankl's (1985) work on meaning making will be made in group discussion. Activity scheduling worksheets from Martell, Dimijian and Herman-Dunn (2013) will be used for out of session homework.

We plan two phases for the study. The first phase, sessions 1-3, focus on introducing the model of behavioral activation and guide the participants to identify activities that will be pleasant, meaningful, or offer a sense of accomplishment and mastery. The first session aims to normalize diverse responses to health-related stress and loss by introducing the behavioral model of depression, and the rationale for behavioral activation. In the second session participants then clarify their values, so that they can begin scheduling pleasant and/or meaningful activities in the third session. These activities are tailored based on each participant's individual goals, priorities and values. The second phase, sessions 4-6, aims to reinforce and sustain positive gains made via behavioral activation and pleasant activity scheduling. Session 4 offers suggestions for problem-solving ways to overcome unhelpful avoidance, a transdiagnostic vulnerability that sustains a number of emotional and psychiatric disorders. Session 5 offers suggestions for overcoming rumination including instruction in mindfulness, and attentional techniques that help participants attend to the outcomes and experiences of the pleasant activities they engage in. Session 6 concludes the program, and guides participants to consider plans to maintain commitment to pleasant activities.

Prior to beginning the intervention and at the completion of the intervention, surrogates will complete the 1) Hospital Anxiety and Depression Scale (HADS), and 2) Impact of Events Scale Revised (IES-R) questionnaire.

At the completion of the intervention, subjects will participate in another 30-minute phone interview with a study investigator. The study investigator will review the subject's responses to the above surveys and ask follow-up questions. The study investigator will ask how the subject has been coping with any psychological symptoms (i.e. anxiety, depression, post-traumatic stress).

All interviews will be audio recorded and transcribed. Two members of study staff will review the transcriptions and use thematic content analysis to determine the types of psychological symptoms that are present and the reason(s) they may be present.

Outcomes

Part 1- Post-ICU discharge survey and Interview

- Critical Care Family Needs Inventory (CCFNI) questionnaire, a 14-question instrument with each question scored 1-4
- Hospital Anxiety and Depression Scale (HADS), 14-questions each question scored on 0-3 scale.
- Impact of Events Scale Revised (IES-R) questionnaire (measure of PTSD symptoms). This instrument contains 22 questions scored on 0-4 scale.

- Qualitative analysis of interview to determine the prevalence and reason(s) for psychological symptoms

Part 2- Post-ICU discharge survey and Interview

- Each subject's post-intervention HADS score relative to pre-intervention HADS score
- Each subject's post-intervention IES-R score relative to pre-intervention IES-R score
- Qualitative analysis of interview to determine the prevalence and reason(s) for psychological symptoms and effectiveness of the intervention.

When analyzing subject responses, we will account for the following variables

- Whether the patient is deceased or not
- Length of time since hospital discharge
- Whether the subject received mental health services on their own or not
- Whether the subject received daily written summaries in the ICU or not

Statistical Analysis

We expect ~100 subjects to meet inclusion criteria. We expect ~70 to complete Part 1 (Post-ICU discharge survey and Interview). We will determine the prevalence of psychological symptoms and opinions on ICU care by reviewing survey responses and interview recordings. We expect ~30 to complete Part 2 (Post-ICU discharge survey and Interview). We compare pre- to post-intervention survey responses for each subject using a paired t-test. Part 2 will be considered a pilot study. We will use the results to plan a future, adequately powered study.

References

Frankl, V. E. (1985). *Man's search for meaning*. Simon and Schuster.

Hayes, S. C., Strosahl, K. D., & Wilson, K. G. (2011). *Acceptance and commitment therapy: The process and practice of mindful change*. Guilford Press.

Martell, C. R., Dimidjian, S., & Herman-Dunn, R. (2013). Behavioral activation for depression: A clinician's guide. Guilford Press.

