**Tick the box beside the reply that is closest to how you have been feeling in the past week.
Don't take too long over you replies: your immediate is best.**

D	A		D	A	
	I feel tense or 'wound up':			I feel as if I am slowed down:	
3	Most of the time	3		Nearly all the time	
2	A lot of the time	2		Very often	
1	From time to time, occasionally	1		Sometimes	
0	Not at all	0		Not at all	
	I still enjoy the things I used to enjoy:			I get a sort of frightened feeling like 'butterflies' in the stomach:	
0	Definitely as much	0		Not at all	
1	Not quite so much	1		Occasionally	
2	Only a little	2		Quite Often	
3	Hardly at all	3		Very Often	
	I get a sort of frightened feeling as if something awful is about to happen:			I have lost interest in my appearance:	
3	Very definitely and quite badly	3		Definitely	
2	Yes, but not too badly	2		I don't take as much care as I should	
1	A little, but it doesn't worry me	1		I may not take quite as much care	
0	Not at all	0		I take just as much care as ever	
	I can laugh and see the funny side of things:			I feel restless as I have to be on the move:	
0	As much as I always could	3		Very much indeed	
1	Not quite so much now	2		Quite a lot	
2	Definitely not so much now	1		Not very much	
3	Not at all	0		Not at all	
	Worrying thoughts go through my mind:			I look forward with enjoyment to things:	
3	A great deal of the time	0		As much as I ever did	
2	A lot of the time	1		Rather less than I used to	
1	From time to time, but not too often	2		Definitely less than I used to	
0	Only occasionally	3		Hardly at all	
	I feel cheerful:			I get sudden feelings of panic:	
3	Not at all	3		Very often indeed	
2	Not often	2		Quite often	
1	Sometimes	1		Not very often	
0	Most of the time	0		Not at all	
	I can sit at ease and feel relaxed:			I can enjoy a good book or radio or TV program:	
0	Definitely	0		Often	
1	Usually	1		Sometimes	
2	Not Often	2		Not often	
3	Not at all	3		Very seldom	

Please check you have answered all the questions

Scoring:

Total score: Depression (D) _____ Anxiety (A) _____

0-7 = Normal

8-10 = Borderline abnormal (borderline case)

11-21 = Abnormal (case)

Impact of Events Scale Revised (IES-R) questionnaire

INSTRUCTIONS: Below is a list of difficulties people sometimes have after stressful life events. Please read each item, and then indicate how distressing each difficulty has been for you DURING THE PAST SEVEN DAYS with respect to _____ (event)

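### Aim 2 compares families who developed symptoms with those who did not, but this protocol does not systematically record mental health before the admission, so long-standing symptoms can be classed as new

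*Combined protocol and SAP*

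**What the plan says.** Specific aim 2 seeks characteristics of ICU care "associated with the development of psychological symptoms among families". Its method is stated in two sentences: "we analyze phone interviews conducted during and after the hospitalization", and then "We compare themes among families who developed psychological symptoms to those who did not". The plan does not define *developed* against any state before the admission.

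The places where prior mental health could have been recorded are these:

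- **Background.** The parent study is the earliest source of symptom data: "we have measured symptoms of anxiety, depression, and acute stress among family members at multiple time points during the ICU stay". Those measurements begin after the admission.
- **"Exclusion criteria".** The entry is that there are none, so surrogates with earlier illness are in the sample.
- **Part 1 survey, question 4.** "Have you used mental health services since the time the patient was admitted" is the only survey item on the surrogate's own mental health care that names a period, and the period starts at admission. Question 5 asks for an overall impression of such services.
- **Outcomes, variables to be accounted for.** There are four: patient death, time since discharge, receipt of the daily written summaries, and "Whether the subject received mental health services on their own or not". None is prior mental health.
- **Appendix, HADS and IES-R.** HADS asks for the reply "closest to how you have been feeling in the past week". IES-R covers the past seven days, in relation to an event to be written in.
- **Interview guide.** It tells the subject that the interview concerns two periods, the hospital stay and the time since.

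**The concern.** Aim 2 is worded as a question about onset, but the instruments answer a question about current state. A high HADS score at follow-up looks the same in a surrogate who became anxious during the ICU stay and in one who was anxious for years before it. With no pre-admission reference, both fall in the group that developed symptoms.

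Two consequences follow, and they differ in strength.

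1. **Misclassification.** Wherever earlier illness persists to follow-up, the case group contains people whose symptoms are not new. This follows directly from the design.
2. **Possible confounding.** The care themes come from the surrogate's own account. If prior illness raises the symptom score and also colours the description of care, a theme may differ between groups because of history and not because of care. This requires the second link, which is plausible but not shown.

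The listed variable on mental health services does not stand in for history. Question 4 pools treatment already under way at admission with care newly sought. New care-seeking can itself result from symptoms. A negative answer does not rule out past or untreated illness.

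The point bears on Aim 2. Aim 1 asks how common current symptoms are, and Part 2 compares each subject with their own pre-intervention score. Neither needs to establish onset.

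**Working it through.** The plan states no figure on this point, so there is none to reproduce. The textual check is the list above: no element of this protocol systematically asks about the time before admission. The rest is illustration. Every input is assumed except the expected Part 1 sample of about 70 (Statistical Analysis).

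**Step 1. Share of symptomatic surrogates with any prior history.** Let h be the proportion with a history, r1 = 0.70 the symptom prevalence with a history, and r0 = 0.40 the prevalence without.

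Share = h·r1 / [h·r1 + (1 − h)·r0]

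- h = 0.10: 0.07 / (0.07 + 0.36) = 0.07 / 0.43 = 16%
- h = 0.20: 0.14 / (0.14 + 0.32) = 0.14 / 0.46 = 30%
- h = 0.30: 0.21 / (0.21 + 0.28) = 0.21 / 0.49 = 43%

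**Step 2. Excess linked to history.** A person with a past, resolved illness can have a new episode. On these inputs, 40% of those with a history would be symptomatic at the no-history rate, so only the difference r1 − r0 = 0.30 is linked to history.

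Excess share = h·(r1 − r0) / [h·r1 + (1 − h)·r0]

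- h = 0.10: 0.03 / 0.43 = 7%
- h = 0.20: 0.06 / 0.46 = 13%
- h = 0.30: 0.09 / 0.49 = 18%

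**Step 3. The same in people, for 70 completers.**

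| h | Symptomatic | With any history | Excess linked to history |
|---|---|---|---|
| 0.10 | 70 × 0.43 = 30.1 | 70 × 0.07 = 4.9 | 70 × 0.03 = 2.1 |
| 0.20 | 70 × 0.46 = 32.2 | 70 × 0.14 = 9.8 | 70 × 0.06 = 4.2 |
| 0.30 | 70 × 0.49 = 34.3 | 70 × 0.21 = 14.7 | 70 × 0.09 = 6.3 |

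**Step 4. Confounding of a care theme with no true effect.** Take h = 0.20, and let 40% of those without a history voice a given complaint about care. Here r1 = 0.70 and r0 = 0.30, a wider contrast than in Step 1.

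- If 40% of those with a history also voice it, the crude odds ratio is 1.00, meaning no confounding.
- If 60% do: symptomatic proportions are 0.18 with the complaint and 0.20 without it; non-symptomatic proportions are 0.26 and 0.36. OR = (0.18 × 0.36) / (0.26 × 0.20) = 1.25.
- If 80% do: the proportions are 0.208 and 0.172, then 0.272 and 0.348. OR = (0.208 × 0.348) / (0.272 × 0.172) = 1.55.

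With r0 = 0.40, as in Step 1, the last two become (0.212 × 0.312) / (0.228 × 0.248) = 1.17 and (0.24 × 0.30) / (0.24 × 0.22) = 1.36.

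The spurious association is therefore nil to moderate, and depends on a difference in complaint rates that the documents do not give.

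**The case against.** The best case for the plan has five parts.

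- **Aim 2 is exploratory and speaks of association.** It compares interview themes, specifies no model and expects about 70 completers. A reader might infer that pre-existing illness is being counted as *caused* by the ICU. The protocol makes no causal claim, so that reading fails. The aim still rests on who developed symptoms, and that classification is what the design cannot support.
- **Confounding is not established.** A reader might infer that prior illness does confound Aim 2. The documents show only that it may: Step 4 gives an odds ratio of 1.00 when complaints are unrelated to history. This objection stands.
- **History can surface in the interview.** A psychologist conducts it and asks follow-up questions, the help-seeking prompts carry no time limit in their own wording, and coders look for reasons for symptoms. This is a real but unsystematic route, under a guide that frames only the stay and the time since.
- **IES-R is tied to an event.** This weakens the point for PTSD symptoms. It does not remove it, because items on sleep, irritability and concentration are non-specific. HADS has no such anchor.
- **The parent study may hold the information.** Its forms are not among these documents, so nobody can say from them that history was never recorded, or that it is lost. History can also be asked about at a later contact. A reading that the data are irrecoverable is not supported.

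**Conclusion.** The point holds for this follow-up protocol, as a weakness of Aim 2 that should be corrected. As written, the plan cannot separate symptoms that arose with the ICU stay from symptoms that preceded it. Misclassification is the firm part, chiefly on HADS. Confounding is a possibility that depends on whether history also affects how care is reported.

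The size is not known. Under the assumed prevalences, 16% to 43% of symptomatic surrogates would have some history, but a reader should not take these for long-standing cases, since they include people who had recovered and then fell ill again. The excess linked to history, 7% to 18% of symptomatic surrogates, is the more relevant pair of figures. It too rests wholly on assumed inputs and is not a direct count of symptoms already present at admission.

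**What to change.** 1. Beside Part 1 question 4, add a two-part item on the time before the patient's admission: whether the surrogate had ever been diagnosed with or treated for anxiety, depression or PTSD, and whether they were receiving care at that time. If the parent study already holds this, link it instead.
2. Add the item to the variables listed under Outcomes.
3. Report Aim 2 overall and, as a sensitivity analysis, by prior history.

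The Part 1 section already foresees an amendment after the first 10 subjects, which would be a convenient vehicle. If that point has passed, a small separate amendment is needed.

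The costs are modest but real. Self-reported history carries recall error, and undiagnosed earlier illness is missed. Subjects already surveyed need a brief re-contact or are analysed as unknown. The subgroup without a history is smaller than the roughly 70 expected: 63, 56 or 49 people if 10%, 20% or 30% have a history (70 × 0.90, 70 × 0.80, 70 × 0.70). The analysis by history should therefore be read beside the overall result and should not replace it.

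### Part 2 is delivered in groups of 3-5, but the only named test treats the ~30 completers as independent, so the precision it reports would be too optimistic if changes correlate within groups

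*Combined protocol and SAP*

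**What the plan says.** The section on the Part 2 intervention describes a "6-week trauma-focused intervention with a psychologist" and sets the format: "We will pilot a group-based intervention (n =3-5) online over Zoom and deliver the intervention across six sessions outlined below". Members interact, since commentary on "work on meaning making will be made in group discussion". Among the stated purposes is "to gather a preliminary estimate of effect size".

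Under Statistical Analysis, the plan says "We expect ~30 to complete Part 2" and names one test: "We compare pre- to post-intervention survey responses for each subject using a paired t-test". It adds "Part 2 will be considered a pilot study" and "We will use the results to plan a future, adequately powered study".

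The Outcomes section lists four variables to be accounted for: whether the patient died, time since discharge, mental health services the subject obtained independently, and receipt of the daily ICU summaries. Therapy group is not listed, and no model is named for using the four. Nothing in the document mentions clustering, an ICC, a mixed model or robust standard errors.

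The delivery format is not uniform across the text. Specific aim 3 describes phone or video counseling without mentioning groups. The Part 1 section says the type of support will be decided, and the protocol amended, after ten subjects have completed Part 1. The document does not say whether the group text already reflects that decision.

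**The concern.** A paired t-test deals with the correlation between a subject's own two scores. It does not deal with correlation between the changes of people who sat through the same six sessions together. A group that works well, or badly, can move its members in the same direction. The ~30 changes then carry less information than 30 independent ones, and the test's standard error is too small.

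The stake is limited but real. Part 2 is meant to yield an effect size for planning a powered study. A planner who asks how firm that effect is will look at the p-value, or at the interval the paired t-test implies. If group membership is not recorded, no group-aware interval can be computed afterwards.

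**Working it through.** **The plan's own figure.** There is none to reproduce. No alpha, power, SD of change, interval width or ICC is given, and ~30 is an enrolment expectation.

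**Inputs from the documents.** n = 30 completers; group size k = 3 to 5, read as size per group. Then 30/5 = 6 groups and 30/3 = 10 groups. Three layouts were examined: 10 groups of 3; six of 4 plus two of 3 (8 groups); 6 groups of 5.

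**Assumed inputs.** ICC of the change scores 0, 0.01, 0.05, 0.10 and 0.20; two-sided 5% level; equal correlation between all members of a group.

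**Standard error.** In units of the SD of change, with equal groups:
- true variance of the mean change = [1 + (k − 1)·ICC]/n
- variance the paired t-test expects = [1 − (k − 1)·ICC/(n − 1)]/n
- reported SE / true SE = square root of the second over the first

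At ICC 0.10:
- groups of 3: √(0.9931/1.20) = 0.910, so the SE is 9.0% too small
- groups of 5: √(0.9862/1.40) = 0.839, so the SE is 16.1% too small

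By hand, for groups of 5: the critical value 2.045 (29 df) acts like 2.045 × 0.839 = 1.716, whose two-sided tail on 29 df is about 9.7%. The simulation gives the same figure.

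**Paired t-test.** Error rates and coverage come from 400,000 simulated trials per cell. The SE shortfall is from the formula above. Shortfall and coverage run from 10×3 to 6×5.

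| Assumed ICC | Type I error, 10×3 / 6×4+2×3 / 6×5 | SE too small by | Coverage of the nominal 95% interval |
|---|---|---|---|
| 0 | 5.0 / 5.0 / 5.0% | 0% | 95% |
| 0.01 | 5.2 / 5.3 / 5.4% | 1-2% | about 95% |
| 0.05 | 6.1 / 6.6 / 7.3% | 4.8-9.0% | 93.9-92.7% |
| 0.10 | 7.3 / 8.2 / 9.7% | 9.0-16.1% | 92.7-90.3% |
| 0.20 | 9.8 / 11.8 / 14.5% | 16.1-26.5% | 90.2-85.5% |

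Repeat simulations agree within a few tenths of a percentage point.

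**What is not affected.** The mean change is unbiased. With a true change of 0.5 SD, the mean estimated standardized effect is 0.513 at ICC 0, 0.515-0.518 at 0.10 and 0.518-0.522 at 0.20. The largest shift is 0.522/0.513 − 1 = 1.8%.

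**Group-aware alternatives.**
- A t-test on the group-mean changes with (groups − 1) df held 4.9-5.1% type I error at every ICC in all three layouts, including the unequal one.
- A random-group model with small-sample df gave 3.1-4.9%, so it is conservative at low ICC. It was checked only for equal groups (10×3 and 6×5).

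**The case against.** The strongest case against is that the planned deliverable is unharmed. Part 2 is a declared pilot meant to give a preliminary effect size. The mean change is unbiased, the standardized effect hardly moves, and no interval, alpha or success threshold is promised. Harm needs both a non-trivial ICC and later reliance on the p-value or interval. This stands, and it keeps the point a suggestion.

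The ICC is also wholly assumed. Group discussion could raise it. Activities tailored to each participant, and a single psychologist running every group if that is what is meant, could lower it. A reader might take the 14.5% error rate as the test's actual error rate. The documents do not support that: it belongs to an assumed ICC of 0.20 with groups of 5, and at 0.01 the excess is negligible.

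The plan does intend to account for four variables in some unspecified way, whereas the calculations model an unadjusted test. That also stands, but therapy group is not one of the four.

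Finally, the pre-post comparison has no control arm and enrols people because they have symptoms. Natural recovery or regression to the mean could therefore produce change, and a group-aware interval repairs neither. True, but this is a separate limit on interpretation and does not make the standard error right.

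**Conclusion.** The point holds as a low-cost improvement. Under the group delivery the protocol describes, the named test gives error bars that are too narrow whenever changes correlate positively within groups. The excess is trivial near ICC 0.01, modest at 0.05 (6-7% error) and material from about 0.10 (7-10%), most of all with groups of 5. This rests on three assumptions: that 3-5 is the size of each group, that there are about 6-10 groups, and that the ICC is positive.

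Two stronger readings are tempting. A reader might infer that the plan states a precision that is wrong. It states none, so the point concerns only what the paired t-test would report. A reader might also infer that the pilot effect size is biased or unusable for planning. The calculations show otherwise.

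**What to change.** Record a therapy-group ID for each Part 2 participant. If delivery is in groups, prespecify one group-aware 95% interval for the change in HADS and in IES-R, reported beside the paired t-test:
- a t-test on group-mean changes with (groups − 1) df, which held its error rate in all three layouts; or
- a random-group model with small-sample df, noting that it was checked only for equal groups.

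The choice is the sponsor's. With unequal groups the two weight subjects differently, which is a reason to fix the choice in advance. Use that interval when judging how firm the pilot effect is. Report the ICC descriptively only: at a true value of 0.10 its estimate is zero or negative in 33-34% of such trials.

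Reconcile specific aim 3 with the Part 2 section on delivery format. If delivery is individual, none of the group-aware analysis is needed.

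**Cost.** One data field and a sentence of analysis text; the paired t-test stays. The group-mean interval is wider than the paired one by about 8-21% at ICC 0, 14-33% at 0.05 and 19-44% at 0.10 (10×3 to 6×5), partly because only 5-9 df are available. The random-group interval at ICC 0 is 13% (10×3) or 23% (6×5) wider. If the group-mean test were used alone, power for a 0.5 SD change at ICC 0 would fall from 75% to 68, 65 or 60% across the three layouts, which is why it should be reported beside the paired t-test and not replace it. Each outcome will then carry two intervals, and the plan should say which one informs the later study.
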